5.1.4.2 Sponsor Follow-Up

For all adverse events, the Sponsor or a designee may follow up by telephone, fax, electronic mail, and/or a monitoring visit to obtain additional case details and outcome information (e.g., from hospital discharge summaries, consultant reports, autopsy reports) in order to perform an independent medical assessment of the reported case. Adverse event follow-up should be documented in the adverse event section of the eCRF.

5.2 SAFETY REPORTING REQUIREMENTS FOR NON-STUDIED MEDICINAL PRODUCTS

Although adverse event information is not being actively solicited for non-studied medicinal products, the investigator/patients are reminded to report any adverse reactions (for which they suspect a causal role of a medicinal product) that come to their attention to the MAH of the suspected medicinal product, or to the concerned competent authorities via the national spontaneous reporting system.

In addition, the following should also be reported if occurring during exposure to a marketed medicinal product, even in the absence of an adverse event:

• Pregnancy

Ocrelizumab—F. Hoffmann-La Roche Ltd 59/Protocol MN42988, Version 3

- Abnormal laboratory findings
- Overdose, abuse, misuse, off-label use, medication error or occupational exposure
- Reports of lack of efficacy
- Product quality defects and falsified medicinal products
- Data related to a suspected transmission of an infectious agent via a medicinal product
- Drug interactions (including drug/drug, drug/food, drug/device, and drug/alcohol)

When a patient is not exposed to a marketed medicinal product, but the physician/consumer becomes aware of the potential for a medication error, or an intercepted medication error, this should also be reported.

5.3 REPORTING OF PRODUCT COMPLAINTS WITHOUT ADVERSE EVENTS

Report Roche product complaints without adverse events, where a product complaint is any written or oral information received from a complainant that alleges deficiencies related to identity, quality, safety, strength, purity, reliability, durability, effectiveness, or performance of a product after it has been released and distributed to the commercial market, to [contact]. Report non-Roche product complaints as per local regulation.

5.4 EXPEDITED REPORTING TO HEALTH AUTHORITIES, PHYSICIANS, INSTITUTIONAL REVIEW BOARDS, AND ETHICS COMMITTEES

The Sponsor will promptly evaluate all serious adverse events and non-serious AESI against cumulative product experience to identify and expeditiously communicate possible new safety findings to investigators, IRBs, ECs, and applicable health authorities based on applicable legislation.

To determine reporting requirements for single adverse event cases, the Sponsor will assess the expectedness of these events using the following reference document:

• Local prescribing information for ocrelizumab (SmPC).

The Sponsor will compare the severity of each event and the cumulative event frequency reported for the study with the severity and frequency reported in the applicable reference document.

Reporting requirements will also be based on the physician's assessment of causality and seriousness, with allowance for upgrading by the Sponsor as needed.

6. STATISTICAL CONSIDERATIONS AND ANALYSIS PLAN

The analysis of this open-label study will be primarily based on descriptive statistical methods. Unless otherwise specified, no statistical tests are planned. Corresponding 95%CIs will be presented as appropriate.

The primary analysis will be performed after the last blood draw at Week 6 to examine B-cell levels in infants. The full analysis, including the analysis of growth velocity of the infants in the first year, will be conducted at the end of the study.

Full details of all statistical aspects and planned statistical analyses will be specified in a separate statistical analysis plan (SAP), which will be finalized prior to the locking of the study database and may include further exploratory analyses not explicitly described in this section.

Analysis Populations

Full analysis set (FAS)

Two separate FAS populations will be considered:

- Women's FAS: this will include all pregnant women defined through the inclusion and exclusion criteria in the study who were exposed to ocrelizumab either 0–6 months before the last menstrual period or in the first trimester of pregnancy (i.e., up to gestational Week 13 [inclusive]).
- Infants' FAS: includes all infants born to women in the FAS who were potentially exposed to ocrelizumab during pregnancy.

Safety Population

The safety population for the women is the same as the FAS. The safety population for infants will include all infants of mothers in the FAS population.

6.1 DETERMINATION OF SAMPLE SIZE

The study will include approximately 33 pregnant women.

There is no formal sample size calculation, as no confirmatory hypothesis testing is planned. The primary analysis will be descriptive. Considering a 10% dropout rate, *approximately 30* evaluable infants are expected. A further investigation will be performed on the subgroup of infants whose mothers received the last dose of ocrelizumab 0–3 months before the LMP or during the first trimester.

The precisions (width of the two-sided 95% CIs based on normal approximation) for different event rates (an "event" is defined as B-cell levels below LLN) are shown in the following table. If no event is observed from the 30 infants during the study, there is a 95% confidence that the event rate is below 0.114.

Sample Size	Number of Events	Event Rate	Precision
30	1	0.033	0.165
30	2	0.067	0.195
30	3	0.100	0.222
30	4	0.133	0.244
30	5	0.167	0.262

Table 5 Precision at Different Event Rates

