 - Treatment with alemtuzumab within 4 months
 - Treatment with mitoxantrone, methotrexate, of atumumab or cladribine within 6 months

Ocrelizumab—F. Hoffmann-La Roche Ltd

- Treatment with cyclophosphamide *or rituximab* within 12 months
- Treatment with natalizumab within 12 weeks prior to the LMP
- Treatment with teriflunomide within the last two years, unless measured plasma concentrations are less than 0.02 mg/L. If levels are above 0.02 mg/L or not known, an accelerated elimination procedure will be implemented before screening visit. One of the following elimination procedures can be used:
 - Cholestyramine 8 g administered 3 times daily for a period of 11 days, or cholestyramine 4 g three times a day can be used, if cholestyramine 8 g three times a day is not well tolerated
 - Alternatively, 50 g of activated powdered charcoal is administered every 12 hours for a period of 11 days
- Treatment with any investigational agent within 6 months or five half-lives of the investigational drug (whichever is longer) prior to the last ocrelizumab dose or prior to the LMP, whichever occurred first.

STUDIED MEDICINAL PRODUCTS

The study treatment is commercial ocrelizumab. Dosing and treatment duration are at the discretion of the physicians, in accordance with local clinical practice and local labelling (USPI; SmPC).

Statistical Methods

Primary Analysis

The primary analysis will be performed after the last blood draw at Week 6 *of life* to examine B-cell levels in infants.

The proportion of infants with B-cell levels below the LLN will be calculated and the corresponding two-sided Clopper-Pearson 95%CI will be presented.

The B-cell levels at Week 6 of life will be analyzed using descriptive statistics. Mean, corresponding 95% CI, SD, and other statistics will be presented.

Stillbirths and abortions of any type will not be included in the primary B-cell analysis.

Determination of Sample Size

The study will include approximately 33 pregnant women.

There is no formal sample size calculation, as no confirmatory hypothesis testing is planned. The primary analysis will be descriptive. Considering a 10% dropout rate, *approximately 30* evaluable infants are expected. A further investigation will be performed on the subgroup of infants whose mothers received the last dose of ocrelizumab 0–3 months before the LMP or during the first trimester.

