6.4 PRIMARY ANALYSES

6.4.1 Primary Endpoint

The primary analysis will occur once the last infant enrolled has completed the Week 6 of life visit (or equivalent if preterm birth) for B-cell measurement. A sensitivity analysis may be performed; details will be specified in the SAP.

The B-cell levels at Week 6 of life will be analyzed using descriptive statistics. Mean, corresponding 95% CI, SD, and other statistics will be presented. Stillbirths and abortions of any type will not be included in the primary B-cell analysis.

The primary estimand is defined as follows:

• Population: Infants exposed to ocrelizumab up to 6 months before the mother's LMP or during the first trimester (up to gestational Week 13) of pregnancy and not exposed after the first trimester (Infants' FAS).

Ocrelizumab—F. Hoffmann-La Roche Ltd 62/Protocol MN42988, Version 3

• Variable: Binary endpoint if the B-cell level is below LLN.

Note: B-cell reference ranges by week of life (absolute and percentage counts) can be found in Appendix 7.

- Intercurrent events:
 - Withdrawal from the study prior to infant's Week 6 visit missing data will not be imputed
 - Interrupted pregnancy (elective or therapeutic abortion or stillbirth) missing data will not be imputed
 - Fetal complications, or other issues, that render the sample not suitable for measurement of B-*cell levels at Week 6 of life:* missing data will not be imputed
 - Breastfeeding before sample at *Week 6 is taken:*
 - No DMT postpartum while breastfeeding: B-cell data will be included
 - Received any DMT postpartum whilst breastfeeding: B-cell data will be excluded because sample will not be collected
 - Resume OCR postpartum while breastfeeding: B-cell data will be included
 - Infants that were born preterm and whose intervals of assessment were not adjusted (i.e., a baby was born at Week 35, the blood sample needs to be taken at Week 8 (±14 weeks), gestational weeks that would sum up to a full-term baby): B-cell data will be included.
- Population-level summary: Proportion of infants with B-cell below LLN and the two-sided 95% CI will be reported; no formal statistical testing will be done.
- Handling of missing data: No data will be imputed. Every effort will be made to ensure all samples with all supporting information are collected for B-cell measurement.

6.4.2 Secondary Endpoints

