2.2 DETERMINATION OF SAMPLE SIZE

The study will include approximately 33 pregnant women.

There is no formal sample size calculation, as no confirmatory hypothesis testing is planned. The primary analysis will be descriptive. Considering a 10% dropout rate, approximately 30 evaluable infants are expected. A further investigation will be performed on the subgroup of infants whose mothers received the last dose of ocrelizumab 0-3 months before the LMP or during the first trimester

The precisions (width of the two-sided 95% confidence intervals [CIs] based on normal approximation) for different event rates (an "event" is defined as B-cell levels below lower limit of normal [LLN]) are shown in the following table. If no event is observed from the 30 infants during the study, there is a 95% confidence that the event rate is below 0.114.

Sample Size	Number of Events	Event Rate	Precision
30	1	0.033	0.165
30	2	0.067	0.195
30	3	0.100	0.222
30	4	0.133	0.244
30	5	0.167	0.262

 Table 1
 Sample Size Precision at Different Event Rates

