4.4.1 Primary Endpoint

The primary endpoint is binary, defined as the proportion in infants with B cell levels (CD19+ cells, absolute counts) below the LN), measured at Week 6 of life (Yes/No).

The primary estimand is defined as follows:

- Population: Infants exposed to commercial ocrelizumab up to 6 months before the woman's LMP or during the first trimester (up to gestational Week 13) of pregnancy and not exposed after the first trimester (FASI)
- Variable: Binary endpoint, based on whether the B cell level is below the age adjusted LLN.

- Treatment: Commercial ocrelizumab (potential exposure during pregnancy).
- Intercurrent events:
 - Withdrawal from the study prior to infant's Week 6 visit missing data will not be imputed
 - Interrupted pregnancy (elective/therapeutic abortion or stillbirth) missing data will not be imputed
 - Fetal complications, or other issues, that render the sample not suitable for measurement of B cell levels at week 6 of life. – missing data will not be imputed
 - Breastfeeding before sample at week 6 is taken:
 - \circ $\,$ No DMT postpartum whilst breastfeeding: B cell will be included
 - Received any DMT postpartum whilst breastfeeding: B cell will be excluded since sample will not be collected.
 - Resume OCR postpartum whilst breastfeeding: B cell will be included.
 - Infants that were born pre-term and whose interval of assessment was not adjusted (i.e. a baby was born at week 35, the blood sample needs to be taken at week 8 (±14 days), gestational weeks that would sum up to a full term baby): B cell will be included.
- Population-level summary: Proportion of infants with B cell below LLN and the two-sided 95% CI will be reported; no formal statistical testing will be done.

B-cell reference ranges by week of life (absolute and percentage counts) are defined by Borriello et al. 2022 (Appendix 4). B cell data being confounded with illness will be determined by clinical team in a blinded manner before conducting the primary analysis.

4.4.2 Analytical Approach for Primary Endpoint

The proportion of infants with B cell levels at Week 6 of life below the LLN will be analyzed using descriptive statistics. The event rate and corresponding Clopper Pearson 95% CI will be presented. A corresponding listing will be presented for B cell levels (absolute count), including whether any intercurrent events (ICEs) led to exclusion of infant data from the analysis.

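### The planned precision for the primary proportion uses an unnamed normal approximation and is 4–10% narrower than the Clopper-Pearson interval that will be reported

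*Protocol*

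**What the plan says.** Protocol Section 6.1 plans for about 33 women and, after 10% dropout, about 30 evaluable infants. It states that there is no formal sample size calculation because no confirmatory test is planned. In its place, Table 5 gives "The precisions (width of the two-sided 95% CIs based on normal approximation) for different event rates": 0.165, 0.195, 0.222, 0.244 and 0.262 for 1, 2, 3, 4 and 5 events in 30. It adds: "If no event is observed from the 30 infants during the study, there is a 95% confidence that the event rate is below 0.114". The same table and sentence appear in the protocol synopsis, in SAP Section 2.2 (Table 1) and in SAP Appendix 1.

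The interval to be reported is a different one. The protocol synopsis (Primary Analysis, repeated in SAP Appendix 1) says: "The proportion of infants with B-cell levels below the LLN will be calculated and the corresponding two-sided Clopper-Pearson 95%CI will be presented". SAP Section 4.4.2 says: "The event rate and corresponding Clopper Pearson 95% CI will be presented". Protocol Section 6.4.1 names no method: "Proportion of infants with B-cell below LLN and the two-sided 95% CI will be reported".

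**The concern.** The planning interval and the reporting interval are different methods, and neither document says so or explains why. Because there is no power calculation, Table 5 and the zero-event sentence are the only quantitative account of what about 30 infants can show on the primary endpoint. A reader will take the tabulated widths as those the trial is going to deliver.

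There are two further difficulties. First, the label does not identify a formula. Most readers take a normal approximation for a proportion to mean the Wald interval, and that does not reproduce the table. Second, the zero-event sentence does not say whether its bound is one-sided or two-sided, and the exact bound differs noticeably between the two readings.

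Within protocol Section 6, the only method named for the primary proportion is the normal approximation, although Sections 6.4.2 and 6.5 name Clopper-Pearson for other proportions. The omission in Section 6.4.1 looks like an oversight.

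**Working it through.** **Inputs.** n = 30 evaluable infants (33 × 0.9 = 29.7); x = 1 to 5 events; two-sided 95% level, z = 1.96; precision defined as the full interval width. All are from protocol Section 6.1. The reporting method, Clopper-Pearson, is from the protocol synopsis and SAP Section 4.4.2.

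**Step 1: reproduce the stated widths.** Write p = x/n.

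- Wald width: 2z√[p(1−p)/n].
- Wilson score width: 2z√[p(1−p)/n + z²/(4n²)] / (1 + z²/n).

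| Events | Stated | Wald | Wilson |
|---|---|---|---|
| 1 | 0.165 | 0.128 | 0.161 |
| 2 | 0.195 | 0.179 | 0.195 |
| 3 | 0.222 | 0.215 | 0.222 |
| 4 | 0.244 | 0.243 | 0.244 |
| 5 | 0.262 | 0.267 | 0.262 |

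Wald matches no row. Wilson matches rows 2 to 5 to three decimals. Row 1 matches if the Wilson upper limit (0.1667) is kept and the lower limit is replaced by the one-event modification −ln(0.95)/30 = 0.0017: 0.1667 − 0.0017 = 0.1650. The documents mention neither Wilson nor this modification; both are inferred from the figures.

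**Step 2: the interval that will be reported.** The Clopper-Pearson lower limit is the 2.5th percentile of Beta(x, n−x+1), and the upper limit is the 97.5th percentile of Beta(x+1, n−x).

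| Events | Clopper-Pearson 95% CI | Width | Stated | Shortfall | Shortfall, % of Clopper-Pearson width |
|---|---|---|---|---|---|
| 1 | 0.0008–0.1722 | 0.171 | 0.165 | 0.006 | 3.7% |
| 2 | 0.0082–0.2207 | 0.213 | 0.195 | 0.018 | 8.3% |
| 3 | 0.0211–0.2653 | 0.244 | 0.222 | 0.022 | 9.1% |
| 4 | 0.0376–0.3072 | 0.270 | 0.244 | 0.026 | 9.5% |
| 5 | 0.0564–0.3472 | 0.291 | 0.262 | 0.029 | 9.9% |

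Shortfalls are computed before rounding.

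**Step 3: the same gap in infants.** Hold the event rate fixed, allow non-integer event counts in the beta quantiles, and find the smallest n at which the Clopper-Pearson width is no larger than the stated width. The answers are 32, 35, 36, 37 and 37. This is only a way to picture the gap, since the plan sets no precision target.

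**Step 4: zero events in 30.**

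- Wilson, two-sided upper limit: z²/(n + z²) = 0.1135, which rounds to the stated 0.114.
- Clopper-Pearson, two-sided upper limit: 1 − 0.025^(1/30) = 0.116.
- Exact one-sided 95% upper limit: 1 − 0.05^(1/30) = 0.095.
- Exact one-sided confidence attached to 0.114: 1 − (1 − 0.114)^30 = 0.974.

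Read as two-sided, the stated bound is 0.002 too low. Read as one-sided, it is conservative.

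**The case against.** The best case for leaving the table alone has four parts.

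- **The label is not false.** Wilson is itself a normal-approximation interval, so the wording is unspecific rather than wrong, and the arithmetic is sound. This stands: the defect is a mismatch with the analysis and an incomplete label, not a calculation error.
- **Nothing depends on it.** There is no test, no precision target and no sample size derived from the table. This also stands, and it limits the weight of the point.
- **The differences are small where they matter most.** A reader concerned about B-cell depletion looks at the upper limit. There, Clopper-Pearson exceeds Wilson by only 0.005, 0.008, 0.009, 0.010 and 0.012 for 1 to 5 events; in rows 2 to 5 most of the width gap lies in the lower limit. The denominator is also only approximate: with the event count held fixed, going from 31 to 29 infants changes the Clopper-Pearson width from 0.166 to 0.177 for 1 event, and from 0.283 to 0.299 for 5. This is fair. But uncertainty about n moves the width in either direction, whereas the choice of method makes every row look better than it will be.
- **The reporting method is already settled.** The synopsis and SAP Section 4.4.2 name Clopper-Pearson, and SAP Section 4 says that its analyses supersede those in the protocol. So there is no real doubt about what will be reported. It follows that the precision statement should describe that interval, and the SAP itself repeats the approximate widths in Section 2.2.

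**Conclusion.** The concern holds. All five stated widths are narrower than those the planned analysis would give with the same data, by 0.006 to 0.029, or 3.7% to 9.9% of the Clopper-Pearson width. The zero-event bound is nearly right if read as two-sided (0.114 against 0.116), but its method and sidedness are not stated.

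The Clopper-Pearson figures depend only on n = 30 and on the event counts in the table. The identification of Wilson, and of the modified lower limit in row 1, is an inference from the numbers; the conclusion does not need it. The practical effect is modest, and the point is worth correcting mainly because this is the plan's only quantitative statement of precision for the primary endpoint.

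**What to change.** 1. In protocol Section 6.1 (Table 5), SAP Section 2.2 (Table 1) and both copies of the synopsis, replace the precision column with 0.171, 0.213, 0.244, 0.270 and 0.291, and label the widths as Clopper-Pearson instead of normal approximation.
2. In the same four places, replace the zero-event sentence with: *If no event is observed in 30 infants, the upper limit of the two-sided 95% Clopper-Pearson CI is 0.116 (exact one-sided 95% upper limit: 0.095).*
3. In protocol Section 6.4.1, name the two-sided Clopper-Pearson 95% CI, to agree with the synopsis and SAP Section 4.4.2.
4. Optionally, add a descriptive note for reading low counts. The LLN is the 2.5th percentile of the cited reference (protocol Appendix 7), so if that reference applies to this population, about 30 × 0.025 = 0.75 infants would be expected below it. This is not a test.

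The cost is a correction of text and tables, and a slightly less favourable stated precision. The sample size, the analysis and the procedures for women and infants do not change. The protocol edits would have to go through the amendment process in protocol Section 9.7.

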6.2 SUMMARIES OF CONDUCT OF STUDY

Enrollment, screening failures, ocrelizumab administration, and discontinuations from the study will be summarized using descriptive statistics (frequency tables for categorical endpoints and mean, median, range, SD, and 25th–75th quartiles for the continuous endpoints). Subject disposition and the incidence of treatment discontinuation for different reasons will be tabulated. Major protocol violations, including violations of inclusion/exclusion criteria, will also be summarized. All analyses will be performed for overall population.

6.3 SUMMARIES OF DEMOGRAPHIC AND BASELINE CHARACTERISTICS

For women, demographics (age, self-reported ethnicity and educational level), medical history, and neurological examination will be summarized. The following will also be summarized: MS disease history (duration since first MS symptoms, duration of MS since diagnosis, relapses in the past year), baseline measures of EDSS and other important variables.

Characteristics of infants at birth will also be summarized (gender, weight, gestational age at birth and other endpoints collected).

6.4 PRIMARY ANALYSES

6.4.1 Primary Endpoint

The primary analysis will occur once the last infant enrolled has completed the Week 6 of life visit (or equivalent if preterm birth) for B-cell measurement. A sensitivity analysis may be performed; details will be specified in the SAP.

The B-cell levels at Week 6 of life will be analyzed using descriptive statistics. Mean, corresponding 95% CI, SD, and other statistics will be presented. Stillbirths and abortions of any type will not be included in the primary B-cell analysis.

The primary estimand is defined as follows:

• Population: Infants exposed to ocrelizumab up to 6 months before the mother's LMP or during the first trimester (up to gestational Week 13) of pregnancy and not exposed after the first trimester (Infants' FAS).

Ocrelizumab—F. Hoffmann-La Roche Ltd 62/Protocol MN42988, Version 3

• Variable: Binary endpoint if the B-cell level is below LLN.

Note: B-cell reference ranges by week of life (absolute and percentage counts) can be found in Appendix 7.

- Intercurrent events:
 - Withdrawal from the study prior to infant's Week 6 visit missing data will not be imputed
 - Interrupted pregnancy (elective or therapeutic abortion or stillbirth) missing data will not be imputed
 - Fetal complications, or other issues, that render the sample not suitable for measurement of B-*cell levels at Week 6 of life:* missing data will not be imputed
 - Breastfeeding before sample at *Week 6 is taken:*
 - No DMT postpartum while breastfeeding: B-cell data will be included
 - Received any DMT postpartum whilst breastfeeding: B-cell data will be excluded because sample will not be collected
 - Resume OCR postpartum while breastfeeding: B-cell data will be included
 - Infants that were born preterm and whose intervals of assessment were not adjusted (i.e., a baby was born at Week 35, the blood sample needs to be taken at Week 8 (±14 weeks), gestational weeks that would sum up to a full-term baby): B-cell data will be included.
- Population-level summary: Proportion of infants with B-cell below LLN and the two-sided 95% CI will be reported; no formal statistical testing will be done.
- Handling of missing data: No data will be imputed. Every effort will be made to ensure all samples with all supporting information are collected for B-cell measurement.

6.4.2 Secondary Endpoints

Serum concentration of ocrelizumab in the pregnant women/mothers during pregnancy and at delivery, and the serum concentration of ocrelizumab in infants at birth (umbilical cord blood) and at Week 6 of life (or equivalent if preterm birth) will be summarized descriptively.

Mean titers of antibody immune response(s) to vaccinations will be summarized descriptively. The proportion of infants with a positive response (seroprotective titers; as defined for the individual vaccine) to different vaccinations will be calculated and the corresponding two-sided Clopper-Pearson 95% CIs will be presented overall.

Continuous variables at each visit, as well as change from baseline (if applicable) will be analyzed primarily using descriptive statistics. Mean, corresponding 95% CIs, SD, and other statistics will be presented.

Ocrelizumab—F. Hoffmann-La Roche Ltd 63/Protocol MN42988, Version 3

